3.3.4.2 Withdrawal of consent for trial participation

Patients may withdraw their consent for trial participation at any time without the need to justify the decision.

This will however mean that no further information may be collected for the purpose of the trial and negative implications for the scientific value may be the consequence. Furthermore, it may mean that further patient follow up on safety cannot occur.

If a patient wants to withdraw consent, the investigator should explain the difference between treatment withdrawal and withdrawal of consent for trial participation and explain the options for continued follow up after withdrawal from trial treatment, please see [Section 3.3.4.1](#) above.

3.3.4.3 Discontinuation of the trial by the sponsor

Boehringer Ingelheim reserves the right to discontinue the trial overall or at a particular trial site at any time for the following reasons:

1. Failure to meet expected enrolment goals overall or at a particular trial site
2. Emergence of any efficacy/safety information invalidating the earlier positive benefit-risk-assessment that could significantly affect the continuation of the trial
3. Violation of GCP, the trial protocol, or the contract impairing the appropriate conduct of the trial
4. Termination of the development of the compound in this indication.

The investigator / the trial site will be reimbursed for reasonable expenses incurred in case of trial termination (except in case of the third reason).

4. TREATMENTS

4.1 INVESTIGATIONAL TREATMENTS

4.1.1 Identity of the Investigational Medicinal Products

In this trial, the IMP BI 836880 will be switched to a new pharmaceutical formulation which is diluted in a standard 5% Glucose/Dextrose solution. The new formulation will be made available in this trial at the latest before expiry of the old formulation prepared with a drug specific Diluent. Details of the trial medications, BI 836880, ezabenlimab, and respective diluents, are presented in Tables 4.1.1: 1 and 4.1.1: 2, in the IBs for BI 836880 and ezabenlimab as well as in the Instruction for the Pharmacist (IfP).

Table 4.1.1: 1 BI 836880

Substance:	BI 836880
Pharmaceutical formulation:	Solution for infusion
Source:	Boehringer Ingelheim Pharma GmbH & Co. KG
Unit strength:	10 mg/ml (vials with 10 ml)
Posology	rate controlled infusion on Day 1 of each 3-week cycle
Route of administration:	i.v.
Duration of use:	until progression, unacceptable toxicity, or up to a maximum of 53 cycles

Table 4.1.1: 2 Ezabenlimab (BI 754091)

Substance:	Ezabenlimab (BI 754091)
Pharmaceutical formulation:	Solution for Infusion or Concentrate for solution for infusion
Source:	Boehringer Ingelheim Pharma GmbH & Co. KG
Unit strength:	20 mg /mL (15 mL vial) or 20 mg /mL (12 mL vial)
Posology	rate controlled infusion on Day 1 of each 3-week cycle
Route of administration:	i.v.
Duration of use:	until progression, unacceptable toxicity, or up to a maximum of 53 cycles

4.1.2 Selection of doses in the trial

4.1.2.1 Part 1

BI 836880 is currently tested as monotherapy in 2 phase I trials. 29 and 24 patients received BI 836880 in trial 1336.1 (every 3 week schedule) and in trial 1336.6 (weekly schedule), respectively. Dose levels between 40 mg and 1000 mg of BI 836880 were tested in the every 3 week trial. Most commonly reported adverse events were hypertension, asthenia, nausea, vomiting, diarrhea and constipation. 5 DLTs occurred in the two studies (pulmonary embolism, proteinuria, hypertension, respiratory distress). Other relevant adverse events (mode of action related) include peripheral edema and bleeding (epistaxis).

Based on safety data as well as PK and PD analysis, the dose of 720 mg is selected as recommended phase 2 dose (RP2D). This dose will be the highest dose that can be tested in combination with ezabenlimab. The dose below this dose tested in monotherapy trial (360 mg) is safe and showed complete inhibition of systemic targets, and will be used as starting dose for the combination with ezabenlimab. However because of the important safety difference between 360 and 720 mg (mainly occurrence and severity of hypertension), a BI 836880 intermediate dose of 500 mg will be tested. The highest tested dose levels will be expanded before selection of BI 836880 dose to be used for Part 2 of the trial.

In the monotherapy phase I trial (1381.1), a total of 9 patients received ezabenlimab at 3 dose levels (80 mg, 240 mg and 400 mg) in the dose escalation cohorts. There were no DLTs or drug-related SAE reported in any cohort. The most common reported AEs were nausea, fatigue, decreased appetite, constipation and arthralgia. Eight additional patients have been treated at dose of 240 mg in the expansion part of this trial. No grade 4, Grade 5 AE or DLT was reported.

The exploratory analysis of biomarker performed in these 9 patients shows 100% PD-1 receptor occupancy in peripheral blood in all on-treatment patient samples compared to baseline throughout one treatment cycle.

Plasma concentration of ezabenlimab appears to increase linearly (based on AUC0-504h Cmax and Cpre). Furthermore, the observed ezabenlimab PK was compared with model simulated pembrolizumab PK ([R17-2460](#)). Observed ezabenlimab PK profiles overlap with those simulated for pembrolizumab at a dose of 200 mg.

The dose of 240 mg of ezabenlimab once every 3 weeks was chosen to be further explored in monotherapy trials and is recommended as a starting dose in combination trials. The dose level of ezabenlimab will likely be fixed in this study unless safety signals suggest a dose adjustment.

4.1.2.2 Part 2

Once at least 6 patients have received at least 1 cycle at the maximum dose level in Part 1, a safety evaluation of all patients treated in Part 1 will be performed. Based on all available data, the SMC may approve the selected BI 836880 dose (RP2D) to be used in combination

with ezabenlimab for Part 2 of the trial. The RP2D assessment will be supported with the PK and PD analysis of at least 3 patients in each dose cohort.

Update after SMC decision:

The SMC selected the dose BI 836880 720 mg and for ezabenlimab 240 mg as dose for the Part 2 of this trial.

4.1.3 Method of assigning patients to treatment groups

After assessment of all in- and exclusion criteria, each eligible patient will be entered to treatment groups and the appropriate medication number will be assigned. Note that the medication number is different from the patient number (the latter is assigned directly after informed consent was obtained). Site personnel will enter the medication number in the CRF.

4.1.4 Drug assignment and administration of doses for each patient

Medication will be assigned via Interactive Response Technology (IRT) for each treatment cycle. Each medication box does have a unique medication number. To facilitate the use of the IRT, the Investigator will receive all necessary instructions.

The study drug will be prepared and handled according to “Instruction for Pharmacists” which will be filed in ISF. Upon notification a patient entered the study; the pharmacy will prepare the study drug in the assigned dosage for administration to the patient.

Ezabenlimab and BI 836880 will be given every 3 weeks as 2 separate consecutive intravenous infusions by authorized site staff in a specialized unit where emergency care can be provided (e.g. intensive care unit available, medical personal trained in advanced live support) according to “Instruction for Pharmacists”.

The expected infusion time is 60 minutes for ezabenlimab and same for BI 836880; ezabenlimab will be administered first, then 15 minutes (+/- 10 min) after the end of this infusion BI 836880 will be administered.

In case of technical issues or complications during infusion, the total infusion time (including stop time and flushing) for BI836880 should not exceed 360 minutes.

For ezabenlimab, in case of technical issues or complications during infusion, the total infusion time (including stop time) should not exceed 180 minutes.

Appropriate drugs and medical equipment to treat anaphylactic reactions must be immediately available, and study personnel must be trained to recognize and treat anaphylaxis.

In the event of an infusion-related reaction \leq Grade 2, the infusion rate of ezabenlimab may be decreased by 50% or interrupted until resolution of the event and re-initiated at 50% of the initial rate until completion of the infusion. In patients experiencing infusion-related reactions \leq Grade 2, subsequent infusions may be administered at 50% of the initial rate. Depending

on the time of occurrence and the severity of the reaction, the investigator may consider administering additional supportive medication, e.g. corticosteroids for re-introduction. Infusion rate and premedication for further treatment cycles should be adapted according to Investigator decision, but adaption of administration scheme need to be agreed with sponsor. If an infusion related reaction is Grade 3 or higher in severity at any point during the study, treatment with ezabenlimab has to be permanently discontinued.

Premedication:

No premedication will be required for BI 836880 IV or ezabenlimab infusion. If a patient expressed sign of infusion reaction at any BI 836880 treatment, a premedication will be considered for all subsequent treatment infusions (dosage and schedule according investigator's decision) comparable to following scheme:

- Acetaminophen/Paracetamol 650 mg - 1000 mg p.o., or equivalent
- Antihistamine p.o. or i.v., equivalent to Diphenhydramine 50 mg i.v.

Drug re-administration criteria after the first cycle has been completed for Part 1:

Before initiating a new treatment cycle the actual health status will be assessed according to [Flow Chart](#) and described in [Section 5.2.5](#). To continue treatment with further cycles, all of the following criteria must be met:

- No uncontrolled hypertension (according to Exclusion-Criterion #9)
- QTcF <=480 ms (according to Exclusion-Criterion #8)
- Acceptable tolerability (in case of an adverse event at the planned start of a treatment cycle patients may continue therapy only after recovery to a level which would allow further therapy; i.e. CTCAE grade 1 or pre-treatment value or considered not clinically significant)

In case one of the above mentioned criteria is not fulfilled the patient should be re-evaluated for up to 2 weeks. Any case of a delay in treatment cycle should be communicated to the Clinical Monitor at Boehringer Ingelheim. The investigator in agreement with the Clinical Monitor will decide about further treatment of individual patient, based on known risk/benefit of BI 836880 and ezabenlimab.

Rescreening is generally not allowed. In individual cases, rescreening can be considered in alliance with the sponsor.

In case of a DLT (drug related AEs CTCAE Grade 3, 4 according to [Table 5.2.6.1: 1](#)), the patient will discontinue treatment.

Once a DLT has recovered to CTCAE grade 1 or pre-treatment values, the study drugs may be re-started at a lower dose level in case the patients benefit from the study drug after discussion between investigator and Clinical Monitor at Boehringer Ingelheim.

Drug re-administration criteria after the first cycle has been completed in Part 2:

Before initiating a new treatment cycle the current health status of the patient will be assessed according to the [Flow Chart](#).

To continue treatment with further cycles, all of the following criteria must be met:

1. Pre-infusion SBP should be < 160 mmHg and pre-infusion DBP should be < 100 mmHg; study drug administration of both study drugs should be temporarily delayed until BP < 160/100. Please see [Table 10.2.1: 1](#) in [Appendix 10.2.1](#), which describes the guidelines for BP management and study drug administration.
2. QTcF <=480 ms (according to Exclusion-Criterion #8)
3. Echocardiography if clinically indicated (based on investigators judgment) with Left Ventricular Ejection Fraction (LVEF) $\geq 50\%$
4. Acceptable tolerability (in case of an adverse event at the planned start of a treatment cycle patients may continue therapy only after recovery to a level which would allow further therapy in the opinion of investigator).

In case the above mentioned criteria 2, 3, and 4 are not fulfilled, the patient should be re-evaluated as needed. Any case of a delay in treatment cycle should be communicated to the Clinical Monitor at Boehringer Ingelheim. The investigator in agreement with the Clinical Monitor will decide about further treatment of individual patient, based on known risk/benefit of BI 836880 and ezabenlimab.

Dose reduction guidelines

Part 1:

Administration of trial drugs has to be stopped temporarily in case of a DLT (see [Section 5.2.6.1](#)). Patients may continue therapy only after recovery from DLT to at least fulfil retreatment criteria. The future dose of BI 836880 must be a tested dose which is one dose level below the dose received by the patient (Table 4.1.4: 1 and [4.1.4: 2](#) below) Treatment has to be discontinued in case the DLT is not reversible.

Table 4.1.4: 1 Dose reduction recommendations for BI 836880 in Part I

BI 836880 received dose	BI 836880 reduced dose
720 mg	500 mg
500 mg	360 mg
360 mg	Stop BI 836880

In case of AEs (DLTs) that can be definitely characterized as ezabenlimab related, dose can be reduced.

Table 4.1.4: 2 Dose reduction recommendations for ezabenlimab in Part I

Ezabenlimab received dose	Ezabenlimab reduced dose
240 mg	80 mg

For each drug, only one dose reduction will be allowed per patient.

Part 2:

Dose reductions or escalations are not allowed for ezabenlimab in any patient.

In the dose expansion study, only dose reductions/re-escalations are allowed for BI 836880.

Table 4.1.4: 3 Dose reduction recommendations for BI 836880 in Part 2

BI 836880 received dose	BI 836880 reduced dose
720 mg	480 mg

A dose reduction of BI 836880 from 720 mg to 480 mg is allowed, if investigator can attribute the AE unequivocally to the BI 836880 (for e.g., hypertension). If the reduced dose is still intolerable, the dose maybe delayed (please see below the sub-section “Delay of treatment”). If the reduced dose is tolerable, and where deemed in the best interest of the patient, the investigator should re-escalate to the originally assigned dose of 720 mg of BI 836880 as soon as deemed clinically appropriate.

Delay of treatment:

During combination therapy, if treatment is held or discontinued due to an AE(s), both BI 836880 and ezabenlimab will be held or discontinued together. If treatment is to be restarted after resolution (\leq Grade 1 or baseline) of the AE, preferably both BI 836880 and ezabenlimab must be started together.

In some cases, in discussions with the Sponsor, treatment with one of the two investigational drugs can be allowed if there is an AE reported which can be clearly attributed to one of the two drugs and further warrants a temporary discontinuation of this drug in the interest of the patient.

Treatment duration:

Treatment with BI 836880 plus ezabenlimab may continue until disease progression, undue toxicity, withdrawal of patient consent, or 53 cycles [approximately 3 years] from the start of first treatment administration, whichever occurs first. Patients will be allowed to stay on treatment also in the case of initial radiological PD, until progression is confirmed or up to 53 cycles from the start of first treatment administration if the investigator considers that the treatment is beneficial for the patient.

Investigators may consider discontinuing BI 836880 and continue therapy with ezabenlimab for up to 53 cycles from the start of the first treatment administration if the patient has been on therapy \geq 6 months, has achieved at least SD by RECIST 1.1 and can tolerate the therapy, and if the investigator considers this to be in the best interest of the patient.

For any patient still on treatment with the investigational combination of BI 836880 plus ezabenlimab 53 cycles from the start of the first treatment administration, treatment extension will be considered on a case-by-case basis upon request by the investigator for a maximum additional 6 cycles, to complete no later than 30 April 2025, if the investigator considers this to be in the best interest of the patient. After this date treatment with the investigational combination BI 836880 plus ezabenlimab will no longer be available.

Investigators are requested to prepare for discontinuation of patients from the current investigational treatment of BI 836880 plus ezabenlimab and to switch them to alternative available treatment options outside of the current protocol no later than by the final availability date of 30 April 2025.

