3.3.4.1 Withdrawal from trial treatment

An individual patient is to be withdrawn from trial treatment if:

- The patient wants to withdraw from trial treatment, without the need to justify the decision.
- The patient needs to take concomitant drugs that interfere with the investigational product or other trial medication.
- The patient can no longer be treated with trial medication for other medical reasons (such as surgery, adverse events, other diseases, or pregnancy).
- The patient can no longer be treated with trial drug after a drug related Adverse Event CTCAE Grade 4.
- The patient can no longer be treated with trial drug after a DLT, which did not recover to CTCAE Grade 1 or pre-treatment values within 2 weeks (not applicable for part 2)
- The patient has repeatedly shown to be non-compliant with important trial procedures and, in the opinion of both, the investigator and sponsor representative, is not willing or able to stick to the trial requirements in the future.

Given the patient’s agreement, the patient will undergo the procedures for early treatment discontinuation and follow up as outlined in the [Flow Chart](#) (FC) and [Section 6.2.3](#).

For all patients, the reason for withdrawal from trial treatment (e.g. adverse events) must be recorded in the eCRF. These data will be included in the trial database and reported.

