The latest list of “Always Serious AEs” can be found in the eDC system. These events should always be reported as SAEs as described above.

Adverse events of special interest (AESIs)

The term AESI relates to any specific AE that has been identified at the project level as being of particular concern for prospective safety monitoring and safety assessment within this trial, e.g. the potential for AEs based on knowledge from other compounds in the same class. AESIs need to be reported to the sponsor’s Pharmacovigilance Department within the same timeframe that applies to SAEs, please see above.

The following are considered as AESIs:

Dose Limiting Toxicities

All DLTs are considered to be AESIs, and must be reported as such. The definition of DLT is presented in [Section 5.2.6.1](#). DLTs are no longer applicable in Part 2 of the study, therefore are no longer AESIs in Part 2.

Persistent hypertension despite treatment

A hypertensive episode will be considered an AESI if:

- SBP \geq 140 mmHg or DBP \geq 90 mmHg which persists longer than 2 days despite either the initiation of antihypertensive agent(s) in a patient without prior history of hypertension, or the intensification / addition of new antihypertensive agents in a patient with prior history of hypertension.

Immune-related adverse events (irAE)

Although all irAEs are to be reported as AEs, only clinically important irAEs need to be reported as AESIs as defined by the sponsor in [Appendix 10.3](#). Non-clinically important irAEs, such as mild to moderate rash and hypothyroidism, for example, do not need to be reported as AESIs. If an Investigator determines that a severe irAE or other clinically significant irAE that is not included in [Appendix 10.3](#) is medically significant, the investigator may also report this irAE as an AESI.

Recommendations for the management of irAEs are presented in [Appendix 10.4](#).

Infusion-related reactions

All infusion-related reactions need to be reported as AESIs.

In the event of an infusion-related reaction \leq Grade 2, the infusion rate of BI 836880 or ezabenlimab may be decreased by 50% or interrupted until resolution of the event and re-initiated at 50% of the initial rate until completion of the infusion. In patients experiencing infusion related reactions \leq Grade 2, subsequent infusions may be administered at 50% of the initial rate.

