If a patient experiences an infusion-related reaction, acetaminophen and/or an antihistamine (e.g., diphenhydramine) and/or corticosteroid or equivalent medication per institutional standard may be administered prior to subsequent infusions at the discretion of the Investigator for secondary prophylaxis of infusion-related reactions. If an infusion-related reaction is Grade 3 or higher in severity at any point during the study, treatment with BI 836880 or ezabenlimab will be permanently discontinued.

As with any mAb, allergic reactions to BI 836880 and ezabenlimab administration are possible. Appropriate drugs and medical equipment to treat acute anaphylactic reactions must be immediately available, and trial personnel must be trained to recognize and treat anaphylaxis. The trial site must have immediate access to emergency resuscitation teams and equipment in addition to the ability to admit patients to an intensive care unit if necessary.

The following events describe those events that are to be considered potential infusion-related AEs. Regardless of grade, these events are considered as AESIs and must be reported within 24 hours of the event:

- Allergic reaction
- Anaphylaxis
- Cytokine-release syndrome
- Serum sickness
- Infusion reactions
- Infusion-like reactions

If the Investigator determines that another event (not on the list) may be a potential infusion related AE, the Investigator must report that event as an AESI.

Potential DILI

A potential DILI is defined by the following alterations of hepatic laboratory

- Parameters:
 - **For patients with normal aminotransferase levels at baseline:** an elevation of AST and/or ALT ≥ 3 fold ULN combined with an elevation of total bilirubin ≥ 2 fold ULN measured in the same blood draw sample and without evidence of cholestasis, OR aminotransferase elevations ≥ 10 fold ULN
 - **For patients with abnormal aminotransaminase levels at baseline >1 and <2.5 x ULN at baseline:** An elevation of AST and/or ALT ≥ 3 fold the baseline value combined with an elevation of bilirubin ≥ 2 fold ULN and the baseline value in the same blood sample; OR Aminotransferase elevations ≥ 5 fold the baseline value.

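### For a Grade 3 infusion-related reaction the protocol gives conflicting instructions on which drug is permanently stopped, and the Part 1 DLT table assumes that infusions continue

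*Protocol*

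**What the plan says.** Six places in the protocol bear on what happens after a severe infusion-related reaction.

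- **Section 4.1.4, infusion-reaction text.** At Grade 2 or below, "the infusion rate of ezabenlimab may be decreased by 50% or interrupted until resolution of the event". For a reaction of "Grade 3 or higher in severity at any point during the study, treatment with ezabenlimab has to be permanently discontinued". BI 836880 appears in neither instruction.
- **Section 5.2.7.1, infusion-related reactions.** At Grade 2 or below the text names either drug: "the infusion rate of BI 836880 or ezabenlimab may be decreased by 50" per cent. At Grade 3 or higher, "treatment with BI 836880 or ezabenlimab will be permanently discontinued".
- **Section 4.1.4, *Delay of treatment*.** For patients on both drugs the rule is: "if treatment is held or discontinued due to an AE(s), both BI 836880 and ezabenlimab will be held or discontinued together". An exception, which the site must first discuss with sponsor staff, is worded: "treatment with one of the two investigational drugs can be allowed if there is an AE reported which can be clearly attributed to one". It is confined to an event that "further warrants a temporary discontinuation of this drug in the interest of the patient".
- **Appendix 10.4, general rules.** For the immune-related events it lists, both drugs are stopped, paused or restarted together, and exceptions need the sponsor's agreement. Its list has an entry for infusion-related reactions, which refers back to Section 5.2.7.
- **Section 3.3.4.1.** "The patient can no longer be treated with trial drug after a drug related Adverse Event CTCAE Grade 4".
- **Table 5.2.6.1: 1 (DLT definitions).** A Grade 3 infusion-related reaction is not a DLT if medication controls it and the next infusion is put off by no more than two weeks.

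**The concern.** The two drugs are given as separate consecutive infusions, and the protocol foresees reactions to either. The premedication paragraph of Section 4.1.4 deals with reactions to BI 836880, and Section 5.2.7.1 warns of allergic reactions to both drugs. A rule for a severe reaction therefore has to say which drug or drugs it stops. Here the answer depends on the section consulted.

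Two things are at stake. The first is safety: whether a patient is re-exposed to the drug that caused a severe reaction should not depend on the page a site opens. The second is the Part 1 primary endpoint, the number of patients with a DLT in cycle 1. The DLT exemption and the permanent stop do not fit together, so the same reaction could be classified differently at different sites.

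**Working it through.** The plan gives no figure to reproduce, so the check is a comparison of texts.

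**Step 1. The rules side by side.**

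| Place | Drug stopped | Tied to the causative drug? | Kind of stop |
|---|---|---|---|
| 4.1.4, infusion-reaction text | Ezabenlimab; silent on BI 836880 | No | Permanent |
| 5.2.7.1 | One or the other | Not stated | Permanent |
| 4.1.4, *Delay of treatment* | Both | Only in the exception | Hold or discontinuation; exception temporary only |
| Appendix 10.4, general rules | Both | No; exceptions by agreement with the sponsor | Stop, pause or restart |
| 3.3.4.1 | Trial drug | Event must be drug-related | Withdrawal, Grade 4 |

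**Step 2. Which grade is left open.** Section 3.3.4.1 withdraws the patient from trial treatment after a drug-related Grade 4 event. The conflict is therefore essentially at Grade 3.

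**Step 3. A Grade 3 reaction attributed to BI 836880.**
- The infusion-reaction text of 4.1.4, alone: ezabenlimab stops, and nothing stops BI 836880.
- 5.2.7.1, alone: either drug may be the one stopped.
- *Delay of treatment*: both stop. The single-drug exception does not help, because it covers a temporary discontinuation.
- Appendix 10.4: both stop, unless the sponsor agrees otherwise.

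**Step 4. A Grade 3 reaction attributed to ezabenlimab.** The infusion-reaction text of 4.1.4 stops ezabenlimab and leaves BI 836880 open. Section 5.2.7.1 again stops one unspecified drug. The other two places stop both. Whether BI 836880 may go on alone therefore has different answers.

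**Step 5. The DLT table.** The exemption needs a subsequent infusion within a two-week delay. For the drug that 4.1.4 or 5.2.7.1 stops permanently there is no subsequent infusion. If only one drug is stopped, the table does not say whether an on-time infusion of the other satisfies the condition. The table's re-treatment row makes a related event a DLT when it interrupts either drug for more than 14 days. It does not say whether a permanent stop counts as an interruption. A site that carried on dosing and a site that stopped could thus classify the same reaction differently.

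**Step 6. Scale.** Section 1.4 gives 8 of 81 combination patients with infusion-related reactions or corresponding symptoms: 8/81 = 0.099, or 9.9%, as stated. None was above Grade 3. The count at exactly Grade 3 is not given, so it lies between 0 and 8 of 81 (0% to 9.9%). Nothing in the protocol narrows that range.

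**The case against.** The strongest reply is that the protocol already has a default, stated twice: *Delay of treatment* and Appendix 10.4 stop both drugs together. On that view a permanent stop of ezabenlimab simply triggers the joint stop. The infusion-reaction sentence in 4.1.4 follows a rule about the ezabenlimab infusion rate, so it may be meant for reactions to that infusion. The *or* in 5.2.7.1 may mean whichever drug is running.

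Much of this stands. It shows that the causative drug continues only if 4.1.4's infusion-reaction text or 5.2.7.1 is read without the joint-stop provisions. It does not remove the conflict. The sentence in 4.1.4 is the specific rule and *Delay of treatment* the general one, and a reader may let the specific rule govern. The Appendix 10.4 entry sends the reader back to Section 5.2.7, where the wording is *or*. The two exceptions also differ, since only the one in 4.1.4 is confined to temporary stops.

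A reader might also infer that the conflict contaminates the combination analysis with patients on one drug. The documents do not support that. Section 7.3 bases all Part 2 analyses on the treated set (at least one dose), so every treated patient stays in under any stopping rule. Section 4.1.4 separately allows ezabenlimab alone after at least 6 months with at least stable disease. Retaining these patients is a deliberate choice that does not arise from this wording.

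**Conclusion.** The point holds for Grade 3 infusion-related reactions. Sections 4.1.4 and 5.2.7.1 and Appendix 10.4 give instructions that differ on which drug is stopped, and no precedence is stated. Read alone, the infusion-reaction text of 4.1.4 or 5.2.7.1 would let the causative drug continue. It would go too far to say that the protocol as a whole permits this, or that it does so at Grade 4.

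The DLT exemption presupposes dosing that the permanent-stop rules exclude for the stopped drug. The Part 2 dose has already been selected, so the Part 1 consequence concerns how any such reaction was classified and what enters the rerun of the dose-escalation model planned in Section 7.3.1.1. The protocol does not report whether one occurred.

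A reader might try to project a patient count from the 9.9% and the 290 patients planned for Part 2. That is not supported: the Grade 3 share is not given, and Section 3.2 says planned enrolment will not be reached. The matter was still live when recruitment closed. Section 1.1 reports 44 patients on treatment in January 2022, and Section 4.1.4 allows dosing up to 30 April 2025.

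**What to change.** Reconcile the infusion-reaction text and the *Delay of treatment* paragraph of Section 4.1.4, Section 5.2.7.1, Table 5.2.6.1: 1 and Appendix 10.4 into one rule, stated once and cross-referenced from the other places. The rule should state:

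- which drug or drugs are stopped when the reaction is attributed to BI 836880, to ezabenlimab, or to neither clearly;
- whether continuing on one drug after a permanent stop is allowed, and on whose agreement;
- how the DLT exemption for a controlled Grade 3 reaction applies when a drug is permanently stopped.

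The Grade 2 and below infusion-rate instructions in 4.1.4 and 5.2.7.1 should be aligned at the same time. The sponsor decides the clinical content. For Part 1, confirm whether any Grade 3 infusion-related reaction occurred in cycle 1 and how it was classified before the dose-escalation model is rerun.

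The cost is an amendment to wording, a notice to sites with patients still on treatment, and a short check of existing Part 1 data. No new data collection is needed.
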